5.7.3.2. Other Safety Parameters

5.7.3.2.1. The Columbia Suicide Severity Rating Scale

The Columbia-Suicide Severity Rating Scale (C-SSRS) will be used as a screening tool to prospectively evaluate suicidal ideation and behavior in this study, as part of a comprehensive evaluation of safety. The C-SSRS is an investigator-administered questionnaire that defines five subtypes of suicidal ideation and 4 possible suicidal behaviors, as well as non-suicidal self-injurious behavior and completed suicide.

The baseline is defined as the most severe/maximum score at screening and Week 0. Suicidal ideation and behavior based on the electronic Clinical Outcome Assessment (eCoA) C-SSRS findings ≥ 1 and on any C-SSRS finding reported on the AE CRF, which in the opinion of the investigator is new or considered to be a worsening and clinically significant, will be summarized. Number of participants with treatment-emergent events of suicidal ideation, suicidal behavior, or self-injurious behavior without suicidal intent by worst severity through Week 48 and through Week 156 by ideation/ behavior level will be presented. In addition, summary of change from

baseline to postbaseline worst severity in suicidal ideation, suicidal behavior, or self-injurious behavior without suicidal intent through Week 48 and through Week 156 will be included. Furthermore, participants with positive postbaseline (C-SSRS findings > 0) ideation and behavior through Week 48 and through Week 156 will be presented in a data listing.

5.8. Other Analyses

5.8.1. Pharmacokinetics

PK analyses will be performed on the PK Analysis Set.

5.8.1.1. Serum Guselkumab Concentrations

Blood samples for determining the serum guselkumab concentration will be drawn from all participants according to the Schedule of Activities in the Protocol.

Descriptive statistics of the serum guselkumab concentrations will be calculated by intervention group at each visit, including n, arithmetic mean, SD, median, coefficient of variation (%CV), interquartile range, range (minimum and maximum).

The following analyses will be performed:

- Summary of serum guselkumab concentrations by visit through Week 48 (or up to the time of cross over if applicable)
- Summary of serum guselkumab concentrations by visit through Week 152 (or up to the time of cross over if applicable)
- Proportion of participants without detectable serum guselkumab concentration (below the lower limit of quantification) at each visit through Week 48 (or up to the time of cross over if applicable)
- Proportion of participants without detectable serum guselkumab concentration (below the lower limit of quantification) at each visit through Week 152 (or up to the time of cross over if applicable)
- Summary of serum guselkumab concentrations at each visit by baseline body weight (using quartiles) through Week 48 (or up to the time of cross over if applicable)
- Summary of serum guselkumab concentrations at each visit by baseline body weight (using quartiles) through Week 152 (or up to the time of cross over if applicable)

For patients who had a cross over, additional analyses will be performed:

- Summary of serum guselkumab concentrations by visit from cross over through the end of study (including the PK at cross over visit)
- Proportion of participants without detectable serum guselkumab concentration (below the lower limit of quantification) at each visit from cross over through the end of study (including the PK at cross over visit)
- Summary of serum guselkumab concentrations at each visit by baseline body weight (using quartiles) from cross over through the end of study (including the PK at cross over visit)

5.8.1.2. Pharmacokinetic Data Handling Rules

Unless otherwise specified, the following data handling rules will apply to PK analyses:

- Participants will be analyzed according to the intervention that they actually received.
- All serum concentration summaries for a particular time point will include data obtained from treated participants at the timepoint of interest without imputing any missing data.
- A concentration not quantifiable (below the lower limit of quantification) will be treated as 0 in the summary statistics and shown as the lower limit of quantification (< LLOQ) in the data listings.
- The data from a participant who meets any of the following dosing deviation criteria will be excluded from the by-visit data analyses from that point onwards:
 - Discontinued study intervention.
 - Skipped a study intervention administration.
 - Received an incomplete / incorrect dose.
 - Received an incorrect study intervention.
 - Received an additional dose.

Additional samples excluded from the analysis are described as follows:

- Pre-dose samples collected after the study intervention administration at the time of visit
- Pre-dose samples collected before the study intervention administration at Week 0, 4, and 8 that were outside of the visit window +/- 4 days
- Samples collected before the study intervention administration after Week 8 through Week 48 that were outside of the visit window +/- 7 days.

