Study Procedure	Screening Visit (within 5 weeks prior to Week 0)								Stu	dy vis	sits (V	Week) ^a	1				Flare visit	Early Termination visit ^{a,d}	Notes
		0	8	16	24	32	40	48	64	80	96	112	128	144 Final dose	152 Final efficacy	156 Final safety			
Stool for enteric pathogens																	X		For Flare visits: Stool studies for enteric pathogens must include a stool culture and Clostridium difficile toxin assay. Additional testing, such as ova and parasites or Escherichia coli O157:H7 assessment, may be performed at the investigator's clinical discretion.
WPAI-CD		X	X		X			X		X			X		X			X	
PROMIS-29		X	X		X			X		X			X		X			X	
PROMIS Fatigue 7a		X	x		X			X		X			X		X			X	
Crohn's disease- related hospitalizations and surgeries			X	х	х	X	х	х	х	х	х	Х	х	Х	х	х	X	х	Items to be recorded are listed in the healthcare resource utilization worksheet.

Study Procedure	Screening Visit (within 5 weeks prior to Week 0)	Study visits (Week) ^a										Flare visit	Early Termination visit ^{a,d}	Notes					
		0	8	16	24	32	40	48	64	80	96	112	128	144 Final dose	152 Final efficacy	156 Final safety b			
Study Intervention	Administrati	on	Π	Ι	l		l		l	Ī									At the discretion of
Administer (or dispense) study intervention		X	х	x	X	X	X	X	X	X	X	x	X	X					the investigator and participant, and after appropriate and documented training, participants may self-administer study intervention at the investigative site or at home. A caregiver may also be trained to administer study intervention. Starting at Week 48 participants will be given study drug to self-administer the intervening dose (eg, Week 56, 72, 88, 104, 120, 136) dose at home.
Record drug accountability		x	x	x	х	х	х	x	х	x	х	х	x	x	x		x	x	Participants will return study intervention packaging (boxes) when administered at home, for drug accountability, including any unadministered syringes.

- a: Study visits should occur at the specified times post-Week 0 +/- 10 days. Note that while visits out of this window should be documented as a protocol deviation, performing them out of window is preferable to not performing them at all, unless so much time has passed that it is time for the next visit. All assessments described in this table are to be completed prior to study intervention administration, unless otherwise specified. PRO assessments should be completed first, then C-SSRS and then any other clinical procedures, tests, or consultations.

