6.3. Measures to Minimize Bias: Randomization and Blinding

Intervention Allocation

Procedures for Randomization and Stratification

Central randomization will be implemented in this study. At Week 0, participants will be randomly assigned to 1 of 2 intervention groups in a 1:1 ratio (see Section 4.1) based on a

computer-generated randomization schedule prepared before the study by or under the supervision of the sponsor. The randomization will be balanced by using randomly permuted blocks and will be stratified by clinical remission status at baseline (CDAI < 150, CDAI \geq 150), region (North America, Western Europe, rest of world) and number of prior surgeries (1 surgery versus > 1 surgery, with the qualifying surgery counting as 1 surgery). The IWRS will assign a unique intervention code, which will dictate the intervention assignment and matching study intervention kit for the participant.

Blinding

To maintain the study blind, the study intervention container will have a label containing the study name, study intervention number, and reference number. The study intervention number will be entered in the eCRF when the study intervention is dispensed. Each active study intervention and its matching placebo will be identical in appearance and will be packaged in identical containers. All participants will receive the same device(s), which could be either active or matching placebo at 8-week intervals to maintain treatment blinding.

The investigator will not be provided with randomization codes. The codes will be maintained within the IWRS, which has the functionality to allow the investigator to break the blind for an individual participant.

Data that may potentially unblind the intervention assignment (ie, study intervention serum concentrations, anti-guselkumab antibodies) will be handled with special care to ensure that the integrity of the blind is maintained and the potential for bias is minimized. This can include making special provisions, such as segregating the data in question from view by the investigators, clinical team, or others as appropriate until the time of unblinding.

At the Week 48 DBL (main study DBL), data will be unblinded for analysis to the sponsor only. Treatment assignment will remain blinded to the study sites and participants until the last participant completes the Week 156 evaluations.

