6.4. Study Intervention Compliance

When participants have self- (or caregiver-) administration of study intervention at home, compliance with study intervention will be assessed at each visit. Compliance will be assessed via the return of boxes that contained study drug and will then be documented in the source documents and eCRF. Deviation(s) from the prescribed dosage regimen should be recorded in the eCRF.

Participants will receive instructions on compliance with study treatment when they begin self-administration of study intervention at home. When participants begin self-administration at home, the investigator or designated study personnel will maintain a log of all study intervention dispensed and returned.

When study intervention is self-administered by participants (or caregivers) at home, participants will record all study intervention administrations on a diary card.

During the study, the investigator or designated study research personnel will be responsible for providing additional instruction to reeducate any participant who is not compliant with taking the study intervention.

Compliance with the treatment schedule is strongly encouraged. It is understood that treatment may be interrupted for health-related or safety reasons. Therefore, if for any reason a participant cannot receive a dose of study intervention at the scheduled visit, the participant must make every effort to still come in for the scheduled assessments for that visit. In general, the dose should be administered within approximately 2 weeks of that scheduled visit. The participant should then resume the normal study schedule relative to the baseline visit (Week 0). In the case when a participant does not come into the investigational site for a scheduled visit, the site will follow-up with that participant. Due diligence could include telephone calls, certified letters, and email requests. Measures taken to obtain follow-up information must be documented.

Study-site personnel will keep a log of all study intervention dispensed and will compare the amount of study intervention dispensed with the amount returned.

All post-baseline visits up to and including Week 56 will have a visit window of \pm 10 days counting from Week 0 as Day 1. If a study visit occurs outside this window, the Sponsor should be consulted about how the participant should resume his or her normal dose schedule.

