4. POPULATIONS (ANALYSIS SETS) FOR ANALYSIS

5. STATISTICAL ANALYSES

5.1. General Considerations

- Unless otherwise specified, for each study, data from all investigational centers/sites will be pooled for analysis
- Study Day 1 refers to the day of the first study intervention administration. All efficacy and safety assessments at all visits will be assigned a day relative to this day.

Study day for a visit is defined as:

- Visit date (date of Study Day 1) +1, if visit date is \geq date of Study Day 1
- Visit date date of Study Day 1, if visit date < date of Study Day 1

There is no 'Study Day 0'.

- Baseline assessment is defined as the last available assessment collected prior to the first study intervention.
- Descriptive statistics (ie, N, mean, median, SD, IQ range, minimum and maximum) will be used to summarize continuous variables. Counts and percentages will be used to summarize categorical variables. Graphical data displays (eg, line plots) may also be used to summarize the data.

CONFIDENTIAL – FOIA Exemptions Apply in U.S.

- The following conventions will be applied for reporting descriptive statistics of all continuous parameters. For presentation, the mean and median will be presented to 1 decimal greater than the original data, SD will be 2 decimal places greater than the original data, and the minimum and maximum will have the same number of decimal places as the original data.
- The following intervention groups will be presented through Week 48, unless otherwise stated:
 - Placebo
 - Guselkumab

Partial dates for adverse events will be imputed as described in Appendix 11.

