5.1.1. Visit Windows

As participants do not always adhere to the protocol visit schedule, the following rules are applied to assign actual visits to analysis visits. All post-baseline visits up to and including Week 56 will have a visit window of \pm 10 days counting from Week 0 as Day 1. If a study visit occurs outside this window, the Sponsor should be consulted about how the participant should resume his or her normal dose schedule. If a participant has 2 or more actual visits in 1 visit window, the visit closest to the target day will be used as the protocol visit for that visit window. The other additional visit(s) will not be used in the summaries or analyses but they can be used for determination of clinically important endpoints. If 2 actual visits are equidistant from the target day within a visit window, the later visit is used.

All assignments will be made in chronological order. Once a visit date is assigned to a visit window, it will no longer be used for a later time point except for the endpoint.

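### From Week 16, SAP 5.8.1.2 screens PK samples by distance from the nominal visit day instead of time since the preceding dose, so it can drop 56-day troughs and keep 39- to 73-day samples

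*SAP*

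**What the plan says.** SAP 5.8.1.2 has two timing exclusions for PK samples. The early one is "Pre-dose samples collected before the study intervention administration at Week 0, 4, and 8 that were outside of the visit window +/- 4 days". The later one is "Samples collected before the study intervention administration after Week 8 through Week 48 that were outside of the visit window +/- 7 days". I read both as distance from the nominal visit day, because SAP 5.1.1 counts visit windows from Week 0. None of the PK rules mentions time since the previous dose. The listed dosing deviations cover stopped, skipped, incomplete, incorrect and additional doses, but not an early or late one.

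The operational windows are wider. Protocol 1.3, footnote a: "Study visits should occur at the specified times post-Week 0 +/- 10 days". SAP 5.1.1: "All post-baseline visits up to and including Week 56 will have a visit window of" 10 days either way. On a dose missed at its visit, Protocol 6.4 says: "In general, the dose should be administered within approximately 2 weeks of that scheduled visit". It then puts the participant back on the calendar counted from Week 0. Doses are 8 weeks apart (Protocol 6.3): "All participants will receive the same device(s), which could be either active or matching placebo at 8-week intervals to maintain treatment blinding".

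The main Schedule of Activities draws PK at Weeks 0, 8, 16, 24, 32, 48, 96, 128 and 152 and at early termination. It has no Week 4 visit. The only time point four weeks after a dose is a home dose after cross over, with no PK draw. SAP 5.8.1.1 summarizes concentrations by visit through Week 152. SAP 5.8.1.3 relates efficacy to trough quartiles at Weeks 16, 24 and 48, and SAP 5.8.2.2 may compare median troughs by antibody status. Neither section defines a trough by elapsed time.

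**The concern.** A pre-dose concentration is comparable between participants only if the time since the last dose is comparable. Under this protocol the current visit and the previous dose can each move around a fixed calendar, so the interval between them depends on both deviations. The SAP rule looks only at the first. It can discard a sample with the intended interval and retain one that is well short of it or well past it.

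Describing serum guselkumab over time is a stated secondary endpoint. The exposure-efficacy plots and the comparison by antibody status use the same samples under the name of trough. The stray Week 4 suggests that the bullet was not fitted to this schedule. The missing window after Week 48 leaves three visits in the by-visit summaries with no timing check, two of which follow doses taken at home (Weeks 88 and 120).

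**Working it through.** The plan gives no figure to reproduce here, so the check is interval arithmetic.

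**Inputs.** Dosing interval 56 days (8 weeks, Protocol 6.3). Permitted visit deviation -10 to +10 days (Protocol 1.3; SAP 5.1.1). PK windows 4 days up to Week 8 and 7 days from then to Week 48 (SAP 5.8.1.2).

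**Formula.** Days since last dose = 56 + (current visit deviation) - (previous dose deviation).

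**Cases from Week 16, all within the 10-day window:**
- Previous dose +8, current visit +8: 56 + 8 - 8 = 56 days. Excluded, because 8 > 7.
- Previous dose +10, current visit -7: 56 - 7 - 10 = 39 days. Kept.
- Previous dose -10, current visit +7: 56 + 7 + 10 = 73 days. Kept.

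If the previous dose was 14 days late under the two-week allowance in Protocol 6.4, a visit at -7 gives 56 - 7 - 14 = 35 days, also kept.

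**Week 8.** The preceding dose is the first one, and SAP 5.1 states: "Study Day 1 refers to the day of the first study intervention administration". Distance from the nominal day then equals deviation from 56 days, if the first dose was on schedule. Only the 4-day width is at issue. Under even scatter it excludes 12/21 = 57% of compliant visits, and 6/21 = 29% are more than 7 days off and would fail a 56 ± 7 day rule as well.

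**Shares from Week 16.** I enumerated all 21 × 21 = 441 pairs of deviations. With equal weights:
- Excluded now: 6 × 21 = 126, or 126/441 = 28.6%. Of these, 54 lie within 49 to 63 days (54/126 = 42.9%).
- Kept now: 315. Of these, 110 lie outside 49 to 63 days (110/315 = 34.9%).
- Excluded by an elapsed-time rule of 56 ± 7 days: 182/441 = 41.3%. By 56 ± 10 days: 110/441 = 24.9%.

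The documents do not give the scatter of visits. I repeated the count with normal weights truncated at 10 days, taking the two deviations as independent:

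| Assumed scatter | Excluded now | Kept, but >7 days off 56 | Excluded, but within 7 days of 56 | Excluded by 56 ± 7 | Excluded by 56 ± 10 |
|---|---|---|---|---|---|
| SD 3 | 1.2% | 6.9% | 38% | 7.6% | 1.3% |
| SD 4 | 5.2% | 14.9% | 39% | 17.3% | 5.3% |
| SD 5 | 10.1% | 20.8% | 40% | 24.8% | 10.0% |
| Even | 28.6% | 34.9% | 43% | 41.3% | 24.9% |

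**Effect on a concentration.** The half-life is not in the documents. If it is assumed to be 10 to 22 days with simple exponential decline, a 39-day sample reads 2^(17/22) = 1.7 to 2^(17/10) = 3.3 times the 56-day value. A 73-day sample reads about 0.3 to 0.6 times that value.

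**After Week 48.** Weeks 96, 128 and 152 have no timing window. They are 3 of the 8 scheduled post-baseline PK visits.

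**The case against.** The strongest reply is that the consequence is close to nil. SAP Section 1 says that only four participants were enrolled and that the planned analyses no longer apply and are kept for reference. It does promise serum concentrations, but it does not say that these windows govern that report. Trough quartiles of four people mean nothing. This stands, and it sets the severity.

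Second, a visit-day window is a common convention and suits a summary by visit, and no passage defines a trough as 56 days give or take some number. That is fair for the by-visit tables. It does not carry over to 5.8.1.3 and 5.8.2.2, which call these values troughs.

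Third, other provisions help. Protocol 9.4.6.1 excludes data that do not permit accurate PK assessment, and a population PK model would handle varying intervals. But that clause leaves the detailed rules to the SAP, and a population model does not correct the by-visit or quartile outputs.

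Fourth, an elapsed-time rule can cost samples, as the table shows. This is true and belongs in the proposal.

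A reader might also infer that a PK window tighter than the visit window is itself an error, or that no exclusion applies after Week 48. The documents support neither. A tighter PK window is a legitimate choice. The exclusions for samples taken after dosing and for dosing deviations carry no time limit; only the timing window stops at Week 48.

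**Conclusion.** The point holds from Week 16 on. The rule uses the wrong clock for a trough, and deviations that the protocol permits are enough to make it drop a 56-day sample and keep samples at 39 or 73 days. That part needs no assumption. The Week 4 reference and the missing window at Weeks 96, 128 and 152 are matters of text and also stand.

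The size does rest on assumptions. Between about 7% (SD 3 days) and 35% (even scatter) of kept samples are more than 7 days off a 56-day interval. On-interval samples wrongly dropped are fewer: 54/441 = 12% of all samples under even scatter, and 5.2% × 39% = 2% at SD 4. Even scatter is the upper end of this range, not an expectation.

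Two stronger conclusions are tempting and not supported. The 57% at Week 8 does not measure misclassified troughs, because the anchor is right there. Nor do the documents show that the PK results of this study will be materially distorted: four participants were enrolled and the half-life is not given. Severity is minor; this is a cheap improvement.

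**What to change.** Replace the two timing bullets in SAP 5.8.1.2 with one rule. For by-visit and trough summaries before cross over, exclude a sample if the time since the preceding recorded dose lies outside 56 days plus or minus a pre-stated tolerance. Apply it at Weeks 8, 16, 24, 32, 48, 96, 128 and 152, with Week 152 measured from the Week 144 dose. Write samples rather than pre-dose samples, because no dose is given at Week 152. Delete Week 4. The Week 0 sample needs no interval, since no dose precedes it.

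Do not apply the rule to the cross over visit sample, whose date depends on recurrence and which SAP 5.8.1.1 includes expressly, or to the induction visits after cross over. Keep excluded samples in the listings and in the population PK data.

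Choose the tolerance openly. Seven days excludes more than the current rule (17% against 5% at SD 4; 41% against 29% under even scatter). Ten days excludes about the same share as now (5% and 25%) and still screens on the right quantity.

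The cost is SAP wording and one derived variable. The Schedule of Activities already requires actual PK sample times, and Protocol 6.2 has participants record the date and time of home doses. For the four-participant report, listing days since last dose beside each concentration would be enough.
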